6.7 BASELINE, TIME WINDOW, AND CALCULATED VISITS

With regard to efficacy and safety endpoints, the term "baseline" refers to the last observed measurement prior to administration of any randomised study medication. For specific endpoints, baseline definitions are as follows:

Hypoglycaemia rate

The event rate of hypoglycaemia (using the respective endpoint definition) during the 4 weeks prior to randomisation (from Day -28 up to Day -1). Collapsing will be performed as per the rules in [sections 5.4.6.3](#) and [5.4.7](#). Rates will be presented per 30 days and also per patient year.

Insulin dose (total daily, total daily basal or total daily bolus)

Mean daily insulin requirement during the run-in period (Visit 5 to Visit 6, excluding day of randomisation). If < 4 days of valid insulin data is reported during the run-in period then the measurement will be considered missing. For data handling rules see [section 5.4.6.2](#).

Table 6.7: 1 Endpoint specific follow-up period for the assignment to active treatment

Endpoint	Last day of assignment to treatment phase (days after study drug stop date)
Efficacy	
HbA _{1c}	7
Body weight	1
Blood pressure	1
Insulin dose	0
Hypoglycaemia	1
Safety	
Adverse events	7
Hypoglycaemia ^[1]	1

*Refer to [section 5.4.4](#) for the assignment of CGM measurements to the on-treatment period

[1] Refers to all hypoglycaemia analyses except the general hypoglycaemia AE analysis by SOC and PT.

Measurements taken after the last intake of study drug and after the end of the endpoint specific follow-up period will be considered off-treatment values.

Efficacy, safety, will be assigned to visits based on time windows around the planned visit dates. These time windows are defined based on the planned number of days after the date of first administration of study drug (see [table 6.7: 2](#)).

Table 6.7: 2 Time windows for HbA_{1c} measurements at scheduled visits after randomisation

Visit number	Visit label	Planned days	Time window (actual days on treatment)	
			Start	End ^A
6	Baseline	0	NA	1 ^B
8	Week 4	28	2	56
9	Week 12	84	57	105
10	Week 18	126	106	154
12	Week 26	182	155	241
14	Week 43	301	242	332
16	Week 52/EOT	364	333	Study drug stop date + X days

^A In case of premature discontinuation of the study drug an eEOT visit has to be performed. Measurements from the eEOT visit will be assigned to the appropriate visit according to the table. In this case the time window for the visit that includes the eEOT visit will end X days after the study drug stop date, including Day X. The definition of X is endpoint specific, cf. [table 6.7: 1](#). Patients will then be asked to continue in the study according to the visit schedule. Off-treatment measurements will be assigned to visits in the same manner. No time window for optional visit is planned.

^B Only values taken prior to the start of treatment with randomised study drug can be considered baseline values. Time windows will be used for assignment of measurements to scheduled visits.

The mid-point between two visits defines the end of a time window, with the midpoint being included in the time window of the preceding visit. The end of the time window of the last on-treatment visit (end of treatment (EoT)) is endpoint dependent (cf. [table 6.7: 1](#)). As endpoints are planned to be measured according to different visit schedules, this midpoint algorithm will be applied and the time windows modified accordingly.

For example, the time windows for the blood pressure endpoints have been detailed in [table 6.7: 3](#).

Table 6.7: 3 Time windows for blood pressure measurements at scheduled visits after randomisation

Visit number	Visit label	Planned days	Time window (actual days on treatment)	
			Start	End ^A
6	Baseline	0	NA	1 ^B
7	Week 1	7	2	17
8	Week 4	28	18	56
9	Week 12	84	57	105
10	Week 18	126	106	154
12	Week 26	182	155	210
13	Week 34	238	211	269
14	Week 43	301	270	318
15	Week 48	336	319	350
16	Week 52/EOT	364	351	Study drug stop date + X days

^A In case of premature discontinuation of the study drug an eEOT visit has to be performed. Measurements from the eEOT visit will be assigned to the appropriate visit according to the table. In this case the time window for the visit that includes the eEOT visit will end X days after the study drug stop date, including Day X. The definition of X is endpoint specific, cf. [table 6.7: 1](#). Patients will then be asked to continue in the study according to the visit schedule. Off-treatment measurements will be assigned to visits in the same manner. No time window for optional visit is planned.

^B Only values taken prior to the start of treatment with randomised study drug can be considered baseline values. Time windows will be used for assignment of measurements to scheduled visits.

For insulin endpoints, as data is available on an ongoing basis, a value will be derived using the 14 days prior to drug stop date and time windowing will be applied as outlined above based on the drug stop date. Only data from within the visit window will be used to derive the visit value.

Repeated and unscheduled efficacy and safety measurements will be assigned to the nominal visits and listed in the subject data listings according to the time windows described above. Only one observation per time window will be selected for analysis. For OC analyses, only on-treatment values will be considered. For OC-AD analyses, both on- and off-treatment values will be considered. If there are multiple values within a time-window, the value closest to the protocol planned visit day will be selected. If there are two observations which have the same difference in days to the planned day or if there are two observations on the same day, the earliest value will be used. If an observation is available on the last day of treatment, this observation will be preferably selected over any later observation that is still within the time window. If there are multiple values within the time window of the last visit, including a value on the last day of drug intake, the value on the last day of drug intake is used as the value of the last visit. For the Week 26 primary analysis, this is applicable if study drug is stopped during the time window of the Week 26 visit.

Data prior to randomisation will be based on nominal visits and time windowing will not be applied. For these time points, data from the scheduled visit will always be selected. Unscheduled visits will only be considered if no data from the scheduled visit is available. If no data from a scheduled visit is available and multiple unscheduled values are available for a visit, the first value will be selected.

For standard descriptive tables of laboratory parameters by visit (created by the BI standard macro XLAB2), in case of multiple measurements within a post-baseline time window for a visit, the worst value of these multiple measurements will be used for calculations.

Note: for LOCF imputation, the last observed on-treatment value will be carried forward, whether or not it was selected in the previous time window. Also for interpolation any valid values can be used, regardless of whether they were selected as visit values. For more details on LOCF refer to [section 6.6](#).

7 PLANNED ANALYSES

Disposition of the patient population participating in the trial will be analysed by treatment groups and presented in the clinical trial report as a frequency-distribution.

The overall disposition information will be presented as well as the disposition status at week 26.

The number of patients participating (screened, randomised, screened but not randomised, etc.) in the study by region, country and, for treated patients, centre, will also be analysed by treatment group and presented as a frequency distribution. The reason for not randomising screened patients will also be summarised. See [table 9.1: 1](#) for assignment of countries within region.

In addition, the number of patients who discontinued trial medication due to fatal and non-fatal adverse events will be displayed in Appendix 16.1.9.2, as well as the number of screened patients by country and the number of screened patients by age groups. These analyses will be done for public data disclosure on European Union Drug Regulating Authorities Clinical Trials (EudraCT).

A summary of the number of patients in each randomisation stratum per treatment will also be shown. This summary will be based upon the data received from the IxRS provider.

For efficacy analyses, patients will be analysed according to the stratum to which they belong (regardless of any mis-assignment based on identification of the wrong stratum). For patients who were mistakenly randomised on both MDI and CSII at baseline, the stratification factor from IxRS will be used.

These two IPV analyses will be presented at week 26 and an additional overall IPV table will be created to summarize all the IPV's up to week 52.

For in-text tables presenting descriptive analysis of the endpoints and other variables (analysed in original scale), the set of summary statistics is: N (number of patients with non-missing values), mean, standard deviation (SD).

For End-Of-Text (EoT) tables, the set of summary statistics is: N (number of patients with non-missing values) / Mean / SD / standard error (SE) / Min / Q1 (lower quartile) / Median / Q3 (upper quartile) / Max.

For the in-text, end-of-text and appendix tables presenting descriptive analysis of the endpoints and other variables (analysed on logarithmic scale), the respective summary statistics (e.g., gMean, gCV, etc.) will be used.

Statistical parameters will be displayed to a defined number of decimal places as specified in the BI guideline "Reporting of Clinical Trials and Project Summaries" ([7](#))

Tabulations of frequencies for categorical data will include all possible categories and will display the number of observations in a category as well as the percentage (%) relative to the respective treatment group (unless otherwise specified, all patients in the respective patient set whether they have non-missing values or not). Percentages will be rounded to one decimal place. The category missing will be displayed only if there are actually missing values.

Treatment comparison

In all specified statistical analyses, treatment comparisons will be made between each randomised Empagliflozin group (10 and 25 mg) and placebo.

7.1 DEMOGRAPHICS AND OTHER BASELINE CHARACTERISTICS

7.1.1 Baseline evaluation

Descriptive analysis of the following demographic variables measured at baseline will be presented:

Sex, race, ethnicity, region, age (years), age-groups, BMI (kg/m^2) categories, height (cm), smoking history and alcohol status, time since diagnosis of diabetes (years) (continuous and in categories), eGFR by CKD-EPI creatinine equation (continuous and in categories) and eGFR by CKD-EPI creatinine-cystatin C (continuous and in categories).

See [section 7.8.2.4](#) for details on the derivation of eGFR endpoints.

Descriptive analysis of the following variables measured at baseline will be presented:

HbA_{1c} (%) (continuous and in categories), FPG (mg/dL) (continuous and in categories), weight (kg) (continuous and in categories), waist circumference (cm), blood pressure (mmHg) (continuous and in categories), UACR (mg/gcrea) (continuous and in categories), fasted serum BHB (mmol/L) (continuous and in categories), capillary daily patient self-measured BHB (mmol/L) (continuous and in categories) and capillary morning patient self-measured BHB (mmol/L) (continuous and in categories).

Baseline hypoglycaemia rates will be presented in a separate table, displaying both the rate (per 30 days) and the frequency (from day -28 to day -1, inclusive) of 'severe hypoglycaemia events confirmed by adjudication' and 'symptomatic hypoglycaemia AEs with confirmed plasma glucose $<54\text{mg}/\text{dL}$ and/or severe hypoglycaemia events confirmed by adjudication'. For the rates, the statistics will include the number of patients overall (N), the number of patients with at least 1 event (Nh), mean, SD, SE, min, 5th percentile (P5), P10, P25, median, P75, P90, P95, and max.

A separate table will display baseline CGM variables, including time spent in target glucose range of >70 to ≤ 180 mg/dL (%), time spent in hypoglycaemia (%), time spent in hyperglycaemia (%), IQR, MAGE, %CV, hourly mean area under the median curve over 24 hours.

Categories for baseline characteristics are defined in [section 6.4](#).

Demographic and baseline characteristics tables will be presented on the FAS.

The demographic analysis will be repeated on the randomised population in Appendix 16.1.9.2 for disclosure on EudraCT.

7.2 CONCOMITANT DISEASES AND MEDICATION

Only descriptive statistics are planned for this section of the report using the FAS.

Concomitant medication use will be summarised by Anatomical-Therapeutic-Chemical classification level 3 (ATC3) and preferred name. Summaries will be presented for concomitant therapies taken during randomised treatment and those taken at baseline.

The summary on concomitant therapies during randomised treatment will be presented up to week 26 as well as up to week 52.

Separate summaries of use of antihypertensives, ASA or lipid lowering drugs at baseline by preferred name will be presented. The displayed categories and defining ATC levels and ATC codes are shown in [table 9.2: 1](#).

Background pre-existing insulin therapy, including a categorisation of patients using MDI versus CSII will be presented. This summary will include background total daily insulin dose at baseline in insulin 'unit' and 'units/kg' as units of insulin per kg body weight at baseline. The table will also display the total daily basal insulin dose and the total daily bolus insulin dose at baseline. The number of insulin injections at baseline will be presented for MDI patients.

Concomitant diseases will be summarised by MedDRA System Organ Class (SOC) and preferred term (PT). Relevant diabetic medical history will also be presented by treatment group.

7.3 TREATMENT COMPLIANCE

Only descriptive statistics are planned for this section of the report.

Frequency distribution of patients with an overall compliance between 80% and 120% (inclusive) will be reported, as well as patients outside this range.

The overall compliance will be calculated as a weighted average of reported compliance. The sum of all reported compliance over the planned visits (disregarding of run-in) will be divided by the total duration (until last visit where medication is returned).

Refer to [section 6.6.3](#) for how handling a single missing visit date for a compliance record, in the overall compliance calculation.

If compliance is missing at more than one on-treatment visit (>1), the overall compliance will be set to missing.

If a patient has a temporary treatment interruption, this should be reflected in the calculation of compliance.

If a patient prematurely discontinues from treatment, compliance will be calculated until last study drug intake. Missing compliance values for off-treatment visits will not be considered in the calculation for overall compliance.

The compliance analysis will be reported up to week 26 as well as up to week 52.

The FAS patient set will be considered.

7.4 PRIMARY ENDPOINT

7.4.1 Primary analysis

The primary endpoint in this trial is the change from baseline in HbA_{1c} (%) at 26 weeks. Efficacy and effectiveness will be tested in a hierarchical manner.

The primary efficacy analysis will be performed on the FAS (OC). Patients will be assigned to the treatment they were randomised to. Only on-treatment HbA_{1c} values will be included in the primary analysis. Only data up to the Week 26 timepoint will be included. All randomised treatment groups will be included in the same analysis.

Mean changes from baseline in HbA_{1c} after 26 weeks will be analysed using a restricted maximum likelihood-based repeated measures approach (MMRM analysis). Analyses will include the fixed categorical effects of treatment, pre-existing insulin therapy, week and treatment by week interaction, as well as the continuous, fixed covariates of baseline HbA_{1c}, baseline eGFR and baseline HbA_{1c} by week interaction. Patient will be included as random effect. An unstructured (co)variance structure will be used to model the within patient measurements.

If this analysis fails to converge, the following covariance structures will be tested: first-order ante-dependence (ANTE(1)), heterogeneous Toeplitz (TOEPH), Toeplitz (TOEP) and first-order autoregressive (AR(1)). The (co)variance structure converging to the best fit, as determined by Akaike's information criterion, will be used as the primary analysis.

The Kenward-Roger approximation will be used to estimate denominator degrees of freedom. Significance tests will be based on least-squares means using a two-sided $\alpha = 0.025$ (two-sided 97.5% confidence intervals). The residuals are assumed to have a multivariate normal distribution with zero means and covariance matrix as specified above. The primary treatment comparisons will be the contrasts between active treatments and placebo at Week 26.

The statistical model will be:

HbA_{1c} change from baseline = overall mean + continuous baseline HbA_{1c} + pre-existing insulin therapy + continuous baseline eGFR + treatment + week + baseline HbA_{1c} by week interaction + treatment by week interaction + random error

If the null hypothesis is successfully rejected for the efficacy analysis, then an effectiveness analysis will be performed on the mITT (OC-AD), including both on- and off-treatment data. The model will be the same as the model for the efficacy analysis described above.

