# 7.3.1 Primary endpoint analyses

# 7.3.1.1 Primary analysis of the primary endpoint

The primary endpoint in this trial is the change from baseline in HbA1c (%) after 26 weeks.

The primary efficacy analysis will be performed on the FAS; patients will be assigned to the treatment they were randomised to and analysed according to the stratum to which they belong (regardless of any mis-assignment based on identification of the wrong stratum). Only on-treatment HbA1c values will be included in the primary analysis for efficacy.

Mean changes from baseline in  $HbA_{1c}$  after 26 weeks will be analysed using a restricted maximum likelihood-based repeated measures approach (MMRM analysis). Analyses will include the fixed categorical effects of treatment, pre-existing insulin therapy, week and treatment by week interaction, as well as the continuous, fixed covariates of baseline  $HbA_{1c}$ , baseline eGFR and baseline  $HbA_{1c}$  by week interaction. An unstructured (co)variance structure will be used to model the within patient measurements.

If this analysis fails to converge, the following covariance structures will be tested: compound symmetry, variance components and Toeplitz. The (co)variance structure converging to the best fit, as determined by Akaike's information criterion, will be used as the primary analysis.

The Kenward-Roger approximation will be used to estimate denominator degrees of freedom. Significance tests will be based on least-squares means using a two-sided  $\alpha = 0.025$  (two-sided 97.5% confidence intervals). The residuals are assumed to have a multivariate normal

distribution with zero means and covariance matrix as specified above. The primary treatment comparisons will be the contrast between treatments at Week 26.

The statistical model will be:

 $HbA_{1c}$  change from baseline = overall mean + continuous baseline  $HbA_{1c}$  + pre-existing insulin therapy + continuous baseline eGFR + treatment + week + baseline  $HbA_{1c}$  by week interaction + treatment by week interaction + random error

Following the analysis of the efficacy estimand, an effectiveness analysis will be performed on the mITT set. This will use the same model as described for the efficacy analysis, but include all available on- and off- treatment values.

Boehringer Ingelheim BI Trial No.: 1245.69

c03024901-03 Trial Protocol Version 3.0

04 Jan 2017

Page 81 of 144

Page 82 of 144

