4 CHANGE IN THE PLANNED ANALYSIS OF THE STUDY

This TSAP assumes familiarity with changes made via Protocol Amendments, and therefore these changes are not listed here.

The derivation for total daily insulin dose will be based on 14 days prior to the visit rather than 7 days as specified in the CTP.

The back-up covariance structures, to be tested in the event that an MMRM analysis fails to converge using an unstructured covariance structure, have been updated to better fit the trial design and account for unequally spaced visits. Rather than testing compound symmetry and variance components, the following covariance structures will be tested instead: Ante-dependence ANTE(1), heterogeneous Toeplitz (TOEPH) and first-order autoregressive (AR(1)). Toeplitz (TOEP) will continue to be tested as planned.

In CTP amendment 2 (c03024901-03, 4th Jan 2017) the testing strategy was updated and a new graphical illustration added to Section 7.2. Unfortunately, the original illustration was not deleted so both are present. Only the updated illustration is valid.

Changes/adaptations included in the revised version of the TSAP:

-

- Multiple imputation analysis for body weight and blood pressure will include baseline body weight and/or blood pressure respectively as additional effect.

-

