7.5.1.2 Change from baseline in body weight (kg) after 26 weeks

Confirmatory analysis

The analysis of change from baseline in body weight after 26 weeks will follow the strategy for the primary endpoint, MMRM. The model will include the fixed categorical effects of treatment, pre-existing insulin therapy, week and treatment by week interaction, as well as the continuous, fixed covariates of baseline HbA_{1c}, baseline eGFR, baseline body weight and baseline body weight by week interaction. This analysis will be performed on the FAS (OC), including all available on-treatment data up to the Week 26 timepoint.

A descriptive statistics table will present body weight (kg) and body weight change from baseline over time on the FAS (OC, OC-AD).

The treatment response over the treatment period will be illustrated on the FAS (OC) for each visit by plotting the adjusted means (SE) for change from baseline in body weight (kg) at each visit based on the MMRM model. A similar graphic will be created plotting the descriptive mean body weight (kg) at each visit using the FAS (OC).

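### Does naming patient as a random effect beside an unstructured covariance leave the primary HbA1c model ambiguous or unestimable?

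*SAP*

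**What the plan says.** SAP 7.4.1 lists the fixed effects of the primary model and then states: "Patient will be included as random effect. An unstructured (co)variance structure will be used to model the within patient measurements". The displayed equation in the same section has one stochastic term and ends "treatment by week interaction + random error". The section continues: "The residuals are assumed to have a multivariate normal distribution with zero means and covariance matrix as specified above". Degrees of freedom are by Kenward-Roger. The fallback reads "If this analysis fails to converge, the following covariance structures will be tested" and names ANTE(1), TOEPH, TOEP and AR(1), with the choice made by Akaike's criterion.

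Protocol 7.3.1.1 has the same fixed effects, the same equation and the same sentence, "An unstructured (co)variance structure will be used to model the within patient measurements", with no mention of a patient effect. The SAP models for body weight (7.5.1.2), total daily insulin dose (7.5.1.4) and blood pressure (7.5.1.5) follow the primary strategy and list their terms without one. For body weight: "The model will include the fixed categorical effects of treatment, pre-existing insulin therapy, week and treatment by week interaction", followed by the continuous covariates.

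SAP Section 4 says that the fallback list was "updated to better fit the trial design and account for unequally spaced visits", and that "Toeplitz (TOEP) will continue to be tested as planned".

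**The concern.** An unstructured matrix already fits every variance and covariance among the visits freely. A random patient intercept adds one common constant to all of them, so nothing is left for it to estimate. A literal reader would see three difficulties.

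- The section describes its model in two ways: with a patient effect in the text and without one in the equation.
- The information matrix of the covariance parameters, which Kenward-Roger uses, would be singular. The redundancy might also stop the fit from converging, and non-convergence is the trigger for the fallback. Both the efficacy and the effectiveness analysis use this model, and both gate the key secondary endpoints.
- The fallback sentence replaces only the covariance structure, so the intercept might be carried into the fallback models.

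A side issue is that Section 4 justifies the new fallback list partly by unequal visit spacing, whereas TOEPH, TOEP and AR(1) index correlation by visit order.

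**Working it through.** **Inputs.** HbA1c visits up to Week 26 are Weeks 4, 12, 18 and 26 (SAP Table 6.7: 2). The numerical examples use 3 × 225 = 675 patients, from the 225 evaluable per arm in Protocol 7.7. That figure reproduces: a two-sided t-test at 0.025 with difference 0.3 and SD 0.9 needs 225 per arm, with power 0.9005. The documents give no covariance across visits, so those values are assumed and stated below.

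**1. Parameter count.** Four visits give 4 × 5 / 2 = 10 distinct elements. With a random intercept of variance τ the marginal covariance is V = R + τJ, where J is all ones. J is the sum of the ten basis matrices of the unstructured R, so the literal model has 11 parameters of rank 10. This is algebra and needs no assumed values.

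**2. Effect on the fit.** For any τ that keeps R positive definite, R = V − τJ gives the same V and hence the same likelihood. One simulated set used visit SDs 0.6/0.75/0.8/0.9 and adjacent correlations 0.70/0.80/0.75, both assumed.

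| τ | REML log-likelihood | Week 26 contrast | SE |
|---|---|---|---|
| 0 | 204.87516 | −0.251127 | 0.084908 |
| 0.10 | 204.87516 | −0.251127 | 0.084908 |
| 0.20 | 204.87516 | −0.251127 | 0.084908 |

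**3. Kenward-Roger.** V is linear in all 11 parameters, so there are no second-derivative terms. Let I₁₀ be the information matrix for the unstructured model and B the 11 × 10 matrix formed by the identity with a row of ones beneath it. With the intercept added, the information is B I₁₀ Bᵀ and the gradient g of the contrast variance becomes Bg. For any generalised inverse W of B I₁₀ Bᵀ, BᵀWB = I₁₀⁻¹, because B has full column rank. Hence (Bg)ᵀW(Bg) = gᵀI₁₀⁻¹g. The degrees of freedom and the adjusted standard error do not change.

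A numerical check used assumed SDs 0.6/0.8/0.85/0.9, an 8-week correlation of 0.7 decaying with time, and 4% dropout after each of the first three visits:

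| Model | Rank of information | Adjusted SE | df |
|---|---|---|---|
| Unstructured | 10 of 10 | 0.0888033 | 621.543 |
| Unstructured + intercept | 10 of 11 | 0.0888033 | 621.543 |

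**4. Fallbacks, if the intercept were kept.** Parameters without it, then with it (rank): ANTE(1) 7, 8 (8); TOEPH 7, 8 (8); AR(1) 2, 3 (3); TOEP 4, 5 (4). TOEP is again redundant; the other three become different, estimable models. Under the covariance assumed in step 3, with 12% assumed missing at Week 26, keeping the intercept left the Week 26 SE in those three the same to four decimals.

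**5. Spacing.** The HbA1c gaps are 12 − 4 = 8, 18 − 12 = 6 and 26 − 18 = 8 weeks. With an assumed 8-week correlation of 0.7, adjacent correlations are 0.7^(8/8) = 0.70, 0.7^(6/8) = 0.77 and 0.70. For weight (Weeks 4, 12 and 26 in the protocol flow chart) the gaps are 8 and 14 weeks, giving 0.70 and 0.7^(14/8) = 0.54; an assumed 0.5 gives 0.50/0.30, and 0.8 gives 0.80/0.68. ANTE(1) lets adjacent correlations differ and is among the structures that Akaike's criterion compares.

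**The case for a change.** The best argument for a change is that a confirmatory model should be stated once and without ambiguity, and that striking one sentence costs almost nothing. A redundant parameter should not be able to set off the convergence fallback. If the fallback were reached, a literal reader could carry the intercept into ANTE(1), TOEPH or AR(1), where it is a real extra parameter.

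Part of this stands. The sentence is misplaced, the literal model is over-parameterised by exactly one, and in those three fallbacks the two readings are different models. The rest is weaker:

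- The protocol is silent on a patient effect, so there is no contradiction with it. The visible part of SAP Section 4 does not list one, but some of its bullets are blank, so nothing can be inferred from that.
- Under the unstructured matrix the two readings imply the same marginal model, so there are not two primary analyses with different answers.
- A convergence failure caused by the redundancy was not demonstrated. The fallback difficulty needs three steps: the literal reading, failure of the unstructured fit, and retention of the intercept.
- Section 4 gives fit to the design as well as spacing as reasons for its list. It does not claim that every structure serves both.

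**Conclusion.** No change follows. The sentence is a clerical slip, and the section settles its meaning: the equation and the residual statement place all covariance in the random error, which makes patient the subject of the repeated measures. On that reading the model is the protocol's, with 10 covariance parameters, all estimable, and no intercept to carry into a fallback. On the literal reading, the Week 26 contrast, its standard error and the Kenward-Roger degrees of freedom are the same under the unstructured matrix.

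The equality of the fits and the parameter count are exact. The Kenward-Roger result assumes that the software drops the redundant parameter or uses a generalised inverse. The illustrative figures rest on the assumed covariances and dropout; no optimiser was run. The spacing remark concerns a clause of rationale only, since the list already includes a structure that allows for unequal gaps.
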